#### 3.2 Study Groups

A total of 500 participants will be enrolled to receive the vaccine. All participants will be monitored for solicited adverse events for 7 days, unsolicited adverse events for 28 days, SAEs and MAEs for the one year duration of the study, and antibody measurements at baseline, Day 28, Day 84, week 24, and week 52. A subset of 50 participants will have cellular immunity measured at those same intervals.

This protocol amendment provides for unblinding of participants who were entered into the study in the double-blind schedule. For participants who entered the double-blind schedule, the visit process will be as follows:

a) Sites will receive an unblinding list detailing participants who received placebo or study vaccine. Participants who received placebo will be invited to continue in the study under the

open-label study scheme and should make visits from V1.B (first vaccine) onwards, after signing the informed consent, completing visits on day 28 (V2.B), day 56 (second dose) (V3.B), day 84 (V4.B), week 24 (V5.B) and week 52 (V6.B). In this group of participants already enrolled, no antibody dosage collection will be performed at the V1B visit; the V1 values at study entry will be taken. The letter B is added to the visits to differentiate this group of participants who must reorganize the schedule of visits from the administration of the first dose of CoVID vaccine after the unblinding. The procedures for this group are detailed in Table 2.

b) Participants who, after the unblinding, are found to have received study vaccine at the initial visit, will complete the visits established by protocol together with the administration of dose 2 of the study (day 56) onwards, after signing the informed consent. In this group of participants there will be no changes in the nomenclature of the visits.

For both arms (placebo and study vaccine), efficacy contacts are restarted with the second injection visit.

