### 3.4 Procedures

Table 1. In-Person Visits

Intervention		Visit 1	Visit 2	Visit 3	Visit 4	Visit 5	Visit 6
		Day 0 (Screening and First Injection Visit)	Day 28	Day 56 (Second Injection Visit)	Day 84	Week 24	Week 52
Visit window			+/- 7 days	+/- 7 days	+/- 7 days	+/- 14 days	+/- 14 days
Informed Consent		•					
Review Consent		•	•	•	•	•	•
Collect Demographic and Participant Contact Information		•					
Blood sample collected for HIV viral load and CD4/CD8 counts		•				•	•
Urine Pregnancy test- women of childbearing potential		•		•			
Review Inclusion and Exclusion criteria		•		•			

Medical History	●		●				
Check and record prior concomitant medication and vaccines	●		●				
Check and record intercurrent medical conditions	●		●				
Check Contraindications to vaccine	●		●				
Pre-injection vital signs	●		●				
Study group and treatment number allocation	●						
Screening conclusion	●						
Administration of Study Product	●		●				
Safety participant contact (Phone call or in-person visit)			Every 4 weeks (Day 28, 56 and 84 is in person)				
Efficacy participant contact (message) (a)			Weekly from Day 7- week 52 (visit window: +3 days)				
Safety participant contact: in-person visit	●	●	●	●	●	●	●
Paper diary provided to participant	●		●				
E-diary or diary card reviewed with participant and data collected and uploaded to eCRF		●					
Immunogenicity participant contact: in-person visit	●	●	●		●	●	
Blood Sample Collected for ELISA and neutralizing Antibody testing (~25mL)	●	●		●	●	●	
Blood Sample Collection for ICS testing (~30mL) (b)	●	●		●	●	●	
Study conclusion							●

● is used to indicate a study procedure.

(a): If it is preferable, a phone-call or text instead of email for an efficient participant contact is acceptable

(b): In the subset of approximately 50 participants who will have cellular immunity measured

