### **3.6 Immunogenicity In-Person Visits**

Participants will return to the study site on Day 28, Day 84, Week 24, and Week 52 for collection of venous blood samples for antibody testing. Approximately 25mL of serum will be collected for ELISA and neutralizing antibody testing on Day 28, Day 84, Week 24, and Week 52.

In the subset of 50 participants, approximately 30mL of whole blood will be collected on Day 28 and Day 84, and Week 24 and Week 52 for ELISpot testing and intracellular cytokine staining (ICS).

*The visit window for immunogenicity participant contact of Day 28 and Day 84 is +/- 7 days.*

*The visit window for immunogenicity participant contact of Week 24 and Week 52 is +/- 14 days.*

*Telephone visits and face-to-face visits at the same time point can be combined into one face-to-face visit.*

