- **Check and record prior and concomitant medication/vaccines**

Prior medications and concomitant medication/injection must be checked and recorded in the eCRF. Prior medications should include any medication taken by the participant within 14 days prior to screening. Participants will be asked to avoid over-the-counter medications such as antipyretics (e.g., acetaminophen) and anti-inflammatory medications (e.g., ibuprofen, naproxen) in the 12 hours before study vaccine receipt but will be allowed to take these over-the-counter medications as needed to treat fever or other adverse events after vaccination. Usage of these over-the-counter medications will be recorded as concomitant medications and linked to the adverse event collected as solicited or unsolicited events according to the symptom.

- **Check and record intercurrent medical conditions**

Any medical conditions that have arisen are recorded in the eCRF.

- **Treatment number allocation**

The treatment number will be allocated within each step. The number of each administered treatment must be recorded in the eCRF.

- **Injection of study vaccine**

After completing all prerequisite procedures prior to the active vaccine injection, one dose of the assigned vaccine will be administered IM, in the deltoid muscle, preferable of the non-dominant arm. If the investigator or delegate determines that the participant's health on the day of administration temporarily precludes administration, the visit will be rescheduled within 1 week. There will be a 15-minute wait after each vaccination to monitor for any rare anaphylactic reaction. A second injection, of active vaccine Ad5-nCoV, will be administered to all participants on Day 56.

- **Safety participant contacts**

Every 4 weeks there will be telephone calls (Weeks 8-52) to continuously collect any SAE and MAE data. Participants can report any AE they experience at any time during the study period but only SAE and MAE will be entered into the eCRF. Safety participant contacts will occur at First Injection Visit (for 15 minutes post-vaccination), Day 28 (to collect the diary), Day 56 (Second Injection Visit), Day 84 (to collect the diary), Month 4, 5, 6, 7, 8, 9, 10, 11, and 12. Safety participant contacts will be a telephone call for Months 2, 3, 4, 5, 7, 8, 9, 10 and 11, and as an in-person visit on Month 1 (Day 28), Month 2 (Day 56), Month 3 (Day 84), Month 6 (Week 24), and Month 12 (Week 52).

- **E-diary and Diary Cards**

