  - Participants will donate approximately 25mL of whole blood on First Injection Visit, Day 28, Day 84 and Week 24, and Week 52, as described above. Whole blood will be separated into serum, and then aliquoted. These in-person visits will occur at participants' local study site. A baseline antibody titer against SARS-CoV-2 will be established from the blood sample collected on First Injection Visit, as outlined in the "baseline serology" description. In addition, these samples will also be used to evaluate for additional immunogenicity objectives. Serum collected will be analyzed for the seroconversion rate of S-RBD IgG antibody, GMT of S-RBD IgG antibody, GMI of S-RBD IgG antibody, seroconversion rate of pseudo-virus neutralizing antibody, GMT of pseudo-virus neutralizing antibody, and the GMI of pseudo-virus neutralizing antibody at Day 28, Day 84, Week 24, and Week 52. The second aliquot will be shipped by the central laboratory to Nexelis Laboratories, where it will be stored as a back-up.
  - **Blood collection for ELISpot and ICS measurement**
    - In a subset of approximately 50 participants, approximately 30mL of whole blood will be collected from participants on First Injection Visit, Day 28, Day 84 and Week 24, and Week 52, as described above. TNF, IL-4, IL-5, IL-13 will be measured by ICS on Day 28, Day 84 and Weeks 24 and 52 after vaccination. PBMC will be shipped on dry ice to Nexelis Laboratories (Canada).

- **Final serology**

Participants will have an in-person visit on Month 12. Approximately 25 mL of whole blood will be collected from each participant and separated for serum into two aliquots. The first aliquot will measure antibodies against SARS-CoV-2, at Nexelis laboratories. The second aliquot will be shipped by Nexelis laboratories to the Sponsor, where it will be stored as a back-up. The one-year antibody levels measured against SARS-CoV-2 will be compared to

the participant's baseline levels to evaluate the exploratory efficacy analysis against asymptomatic infection.

*The visit window for immunogenicity in-person visits of Day 28 and Day 84 is +/- 7 days.  
The visit window for immunogenicity in-person visits of Week 24, and Week 52 is +/- 14 days*

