# 6. STUDY PRODUCT AND ADMINISTRATION

## 6.1 Description of Study Product

Recombinant Novel Coronavirus Vaccine (Adenovirus Type 5 Vector). This vaccine, Ad5-nCoV, is a replication-defective recombinant human type 5 adenovirus expressing novel coronavirus S protein, which is produced by viral amplification in HEK293SF-3F6 cells, purification and formulation with addition of proper excipients. The product is used for prevention from infection caused by novel coronavirus.

**Active Ingredients:** Replication-defective recombinant human type 5 adenovirus expressing S protein of novel coronavirus

**Excipients:** Mannitol, sucrose, sodium chloride, magnesium chloride, polysorbate 80, HEPES, and glycerin

**Packaging:** The vaccine is contained in a vial.

**Specification:** 0.5 mL/vial

**Dosage**  $5 \times 10^{10}$  vp ( $\geq 4 \times 10^{10}$  vp)

\* Explanatory note: The vials contain a volume of 0.5 ml. The indication is to administer this amount. The manufacturer of the vaccine has advised that a volume between 0.4 ml and 0.5 ml per dose is permitted since it has been calculated that the 0.4 ml extractable volume of each vial in the lot involved in this study (Lot NCOV202103006) has met the requirements of the study based on good vaccination practices. The vaccines used in this study have passed the quality control procedure during the filling process and the fill volume of the vaccines meets the quality standards.

**Shelf Life:** Tentatively 24 months

**Storage:** This vaccine should be stored and transported at 2-8°C.

**Administration:** Intramuscular injection in the deltoid muscle of the upper arm.

**Schedule:** A double-dose of active vaccine is planned for all participants. A second dose of active vaccine is planned for all participants 56 days after the first Injection.

**Manufacturer:** CanSino Biologics Inc.  
[name]  
Postal code: 300462  
[contact]  
[contact]  
Website: [www.cansinotech.com](http://www.cansinotech.com)

**Developers:** CanSino Biologics Inc.  
Beijing Institute of Biotechnology

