**7.2 Detection of adverse events**

All participants will be instructed on the recognition of symptoms and signs by the study staff. Monitoring for any signs or symptoms of COVID-19 is instrumental in evaluating the efficacy of

the candidate vaccine. Participants will be monitored for incidence of local and systemic AE, in addition to monitoring for SAE. These participants will be instructed on how to take their temperature orally, as well as to record any symptoms in their e-diary or diary card for 28 days after receiving the vaccination. A thermometer and access to an e-diary or a paper diary card will be provided to record solicited AEs from First Injection Visit-Day 7, and unsolicited AEs from First Injection Visit-Day 28. Participants will review their completed e-diary or diary card with study staff at their second in-person visit on Day 28. A second e-diary or a paper diary card will be provided at Day 56 and will be collected at Day 84. Data collected from e-diaries and diary cards will be uploaded into the participant's eCRF. All participants will be monitored for the incidence of SAE and MAE up to 52 weeks after receiving the vaccination, via a phone call every 4 weeks. Participants will be instructed to contact study staff by phone (24 hours a day), if a MAE or SAE occurs.

AE Type	Solicited AEs/ Unsolicited AEs/MAEs/SAEs
Method of 'solicited' participant contact	E-diary or diary card
Method of 'unsolicited' participant contact	E-diary or diary card**
Method for reporting SAEs/MAEs	SAE report forms
Method for reporting pregnancies	Pregnancy report forms

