##### Per-protocol Analysis Cohort

The per-protocol analysis cohort for safety includes subjects in the intent-to-treat who receive the correct treatment, the correct number of doses, and who do not have a major protocol deviation. Detailed definition of this analysis set including definition of major protocol deviations will be described in the Statistical Analysis Plan. The per-protocol analysis cohort for immunogenicity includes subjects in the per-protocol analysis cohort for safety whose samples were drawn inside of protocol specified time windows.

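### Visit 4 is timed from the first injection and not from dose 2, so in-window post-dose-2 samples span 14 to 42 days and the dose-2 diary can be collected early

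*Protocol*

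**What the plan says.** Section 6.1 sets the dose schedule: "A second dose of active vaccine is planned for all participants 56 days after the first Injection". Table 1 (section 3.4) counts its columns from Day 0, the first injection, and the windows for Visits 2 to 6 are +/- "7 days +/- 7 days +/- 7 days +/- 14 days +/- 14 days". Day 56 (dose 2) and Day 84 (Visit 4) therefore each have their own 7-day tolerance. Table 2 repeats these windows for former placebo recipients, counted from their own first active dose. Section 3.6 says "The visit window for immunogenicity participant contact of Day 28 and Day 84 is +/- 7 days", and section 5.1 repeats it: "The visit window for immunogenicity in-person visits of Day 28 and Day 84 is +/- 7 days". None of these places ties the Day 84 window to the date on which dose 2 was actually given.

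The per-protocol immunogenicity cohort (section 9.2.1) keeps those "whose samples were drawn inside of protocol specified time windows".

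On the diary, section 7.2 says "A second e-diary or a paper diary card will be provided at Day 56 and will be collected at Day 84". The synopsis safety endpoints ask for unsolicited events over 28 days after each vaccination. Section 7.2 likewise requires every adverse event that starts in the 28 days after a dose to be recorded.

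Section 3.2(b) covers participants found at unblinding to have received vaccine. They continue the protocol visits with dose 2, labelled day 56, once they have signed the new consent. It adds: "In this group of participants there will be no changes in the nomenclature of the visits". Former placebo recipients, by contrast, get a re-based schedule with the suffix B.

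**The concern.** Visit 4 is the first blood sample after dose 2. It feeds a primary immunogenicity endpoint (seroconversion at Day 84, section 9.3.4) and is the natural sample for the one- versus two-dose question, which is also primary. Two independent windows on a Day-0 clock let the quantity that matters, days since dose 2, vary twice as widely as the corresponding quantity for dose 1. The protocol's background (section 1.2) gives a reason to care: after a single dose, antibodies had risen by Day 14 and peaked at Day 28. Whether the response after a second dose follows the same course is not stated.

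Visit 4 is also where the dose-2 diary is handed in. Once it is collected, Table 3 foresees only serious and medically attended events beyond Day 29, and section 5.1 limits eCRF entry from the safety contacts to those two types. A non-serious event in the third or fourth week after dose 2 may then have no routine way into the data.

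**Working it through.** **Inputs.** Dose 2 at Day 56 +/- 7, so Days 49 to 63. Visit 4 at Day 84 +/- 7, so Days 77 to 91. Visit 2 at Day 28 +/- 7, so Days 21 to 35 (all Table 1).

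**Nominal gap.** 84 - 56 = 28 days, the same as the nominal gap from dose 1 to Visit 2.

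**Range allowed by the windows.** Gap = Visit 4 day minus dose-2 day.

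- Shortest: 77 - 63 = 14 days.
- Longest: 91 - 49 = 42 days.
- Width after dose 2: 42 - 14 = 28 days. Width after dose 1: 35 - 21 = 14 days. The spread is doubled.

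Section 5.1 also allows a deferral when the participant's health "temporarily precludes administration, the visit will be rescheduled within 1 week". I have not added this to the range; I treat it as falling inside the Day 56 window.

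**How often the gap is far from 28.** The protocol gives no distribution. Assume both days are uniform and independent over their 15 permitted days, which gives 15 x 15 = 225 combinations. The gap is outside 21 to 35 days when the two deviations differ by 8 or more: 2 x (7+6+5+4+3+2+1) = 56 combinations. So 56/225 = 25% lie outside and 169/225 = 75% inside.

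**Diary.** Under the same assumption, Visit 4 comes before 28 days after dose 2 in (225 - 15)/2 = 105 of 225 combinations, or 47%. The worst case is 28 - 14 = 14 days early. For the dose-1 diary at Visit 2 the share is 7/15 = 47% as well, but the worst case is only 28 - 21 = 7 days early. The Day-0 clock makes the possible shortfall deeper, not more frequent.

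**Per-protocol filter.** Every combination above has both visits in window, so a rule based on the stated visit windows excludes none of them.

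**Timing from actual dose 2.** 28 +/- 7 gives 21 to 35 days for everyone, equal to the spread after dose 1.

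**Section 3.2(b).** Suppose, as an assumption only, that dose 2 falls L days after Day 56.

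- Visit 4 kept on the Day-0 clock: nominal gap 28 - L. For L = 14, 14 days after dose 2.
- Visit 4 following dose 2: gap stays 28 days, and time since dose 1 becomes 84 + L. For L = 14, 98 days, which is past Day 91 and so outside the stated Day 84 window.

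The text does not choose between them.

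**The case against.** The strongest reply is that this is ordinary windowing. Reaching 14 or 42 days needs the two visits at opposite limits. Under uniform timing three quarters of the gaps lie within 21 to 35 days, actual dates will be on file, and section 9.3 leaves statistical methods to the SAP. All of that is fair and limits the size of the problem. It does not remove it: an analysis can model the timing afterwards, but it cannot move a sample or recover diary entries never made. Visit windows are protocol content, and section 9.2.1 builds the per-protocol set on them.

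Three stronger readings are tempting, and the documents do not support them.

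- A reader might infer from the unchanged visit names that blinded-phase vaccinees received dose 2 late, that some of their Day 84 samples precede it, or that the per-protocol rule drops them. The protocol reports no delay. Section 3.2(b) calls dose 2 day 56 and has the visits continue from there, efficacy contacts restart at the second injection, and Table 1 places Visit 3 before Visit 4. If Visit 4 follows dose 2, the gap stays at 28 days. The intent-to-treat immunogenicity analysis also lacks the window filter.
- A reader might infer that the adverse-event window itself is halved. It is not: sections 7.2 and 7.3 anchor recording and follow-up to 28 days after the dose. What can end early is the diary that serves this duty.
- A reader might take Day 28 against Day 84 as the specified one- versus two-dose comparison. Section 9.3.4 names no pair of visits.

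**Conclusion.** The point holds in a limited form. For all participants, the stated windows allow a compliant post-dose-2 sample 14 to 42 days after dose 2, twice the spread of the post-dose-1 sample, and the per-protocol rule does not filter this out. The range follows from Table 1 alone. The 25% and 47% shares rest on uniform, independent visit timing. How far the spread alters seroconversion or titres cannot be computed, because the protocol gives no time course after a second dose.

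Diary collection at Visit 4 can fall up to 14 days short of the 28-day recording duty. This is a risk to capture, not a change in the duty.

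For unblinded vaccinees the finding is only that the governing clock for Visits 4 to 6 is unstated should dose 2 fall outside Day 56 +/- 7. Any effect depends on a delay that the protocol does not report.

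**What to change.** 1. In Table 1, Table 2 and sections 3.6 and 5.1, time the Visit 4 sample at 28 +/- 7 days after the actual dose-2 date.
2. In sections 9.2.1 and 9.3.4, define the per-protocol sample window for that visit on days since dose 2.
3. Do not close the dose-2 diary before 28 days after dose 2 have passed. If Visit 4 is earlier, complete the review at an existing telephone contact. For the latest in-window dose 2 this is Day 63 + 28 = Day 91, when section 3.5 already schedules a weekly contact that may be made by phone.
4. Reconcile section 3.2(b) with Table 1 by stating which clock governs Visits 4 to 6 for unblinded vaccinees. This needs no change to, or proposal for, the dosing interval.

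The cost is visit-window wording and one derived variable (days since dose 2). For an in-window dose 2, the centre of the Visit 4 window moves by at most a week, to between 49 + 28 = Day 77 and 63 + 28 = Day 91.
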